Together, these data support our *overarching hypothesis*: that with the same volume of exercise, **HIIT will lead to better physical function and reduced patient-reported fatigue through improvements in mitochondrial bioenergetics compared with CME among older PWH**. We further hypothesize that older PWH randomized to HIIT will maintain self-directed exercise better than those in CME when exercise is no longer supervised, and that behavioral support will help to maintain adherence. Through a three-site (Seattle, WA, Aurora, CO, and Birmingham, AL), clinical trial comparing the clinical and bioenergetic effects of two exercise regimens that vary by interval and intensity (HIIT or CME), we will test our hypotheses through the following aims:

**AIM 1.** Compare the effects of two exercise regimens varying by interval and intensity on *primarily* physical function performance (i.e., 400-m walk time) and *secondarily* on patient-reported fatigue at 16-weeks. We **hypothesize** that PWH randomized to HIIT will experience greater improvements in physical function and reductions in fatigue compared

to CME. **Approach:** We will randomize 180 PWH (aged 50-80 years) into one of two supervised 16-week exercise interventions and compare changes in physical function and patient-reported fatigue over time.

**AIM 2.** Evaluate bioenergetic mechanisms underlying HIIT and CME. We **hypothesize** that PWH randomized to HIIT will have improved mitochondrial bioenergetics (i.e., mitochondrial respiration rate and ETC activity). **Approach:** We will evaluate 16-week changes in skeletal muscle and systemic (peripheral blood mononuclear cells [PBMCs]) mitochondrial activity among PWH in response to supervised exercise.

**AIM 3.** Describe and compare the effect of a biobehavioral coaching intervention to enhance self-directed exercise. **Approach:** After 16 weeks of supervised exercise, HIIT and CME participants will be randomized (in a factorial design) to a 12-week coaching intervention (vs. control) using tailored text messages to support exercise adherence. Physical activity amount (via accelerometry) and experience (via interviews) will be compared between arms using mixed analytic methods.

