The effects of HIIT on physical function in older PWH have not been studied. Evaluation of high-intensity exercise in PWH may be important, as this population appears to have greater impairment in cardiorespiratory capacity (i.e., peak oxygen consumption, VO2peak) compared to age-matched HIV-uninfected controls, with even greater impairments among older PWH with non-AIDS comorbidities. Impaired peripheral oxygen uptake, cardiac response to exercise, or oxygen diffusion capacity related to HIV or exposure to older ART, suggest that PWH may require a different exercise dose to restore and achieve levels of cardiovascular fitness and physical function similar to HIV-uninfected peers. Conversely, these impairments may make exercise more difficult in older PWH, thus undermining their self-efficacy to maintain long-term exercise adherence. But we do not know the answer to these important clinical questions. The 2018 DHHS PA guidelines do not provide specific recommendations for PWH because the evidence base is too scant. *To better inform the dose of exercise needed for maximal benefit in older PWH, we will compare changes in their physical function and fatigue in response to two levels of exercise intensity.*

**Mitochondrial Adaptations.** Among the plausible biological mechanisms underpinning the functional improvements with HIIT, is enhanced mitochondrial function (Figure 1). Mitochondrial activity is directly influenced by the quantity of mitochondrial proteins as determined by the cell's DNA. Yet, as individuals age, there is a decline in mitochondrial DNA and activity. Older age is associated with lower skeletal muscle total mitochondrial DNA mitochondrial mass, enzyme activity (i.e., citrate synthase, cytochrome oxidase), and mitochondrial respiration (Complex I + II) in HIV-uninfected adults. Lower muscle mitochondrial content and impaired activity were

**Figure 1.** Hypothesized skeletal muscle mitochondrial adaptations in response to exercise where mitochondrial respiration is more enhanced in response to HIIT (adapted from Holloway et al, 2018)

associated with older age, lower  $VO_{2peak}$ , and slower walk speed. A physically active lifestyle during older age may preserve mitochondrial function to levels seen in young adults.

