| DXA                                    |                          |    | X                     |    |                             |   |   |   |    | (or X)  | X (ideally before V02)                                    |         |   |   |    |                      |                           |
| 1-RM                                   |                          |    |                       |    |                             | X | X | X | X  |   |   |         |   |   |    |                      |                           |
| Physical Function (FULL)               |                          |    | X                     |    |                             |   |   |   |    | X   |   |         |   |   |    | X                    |                           |
| Physical function (BRIEF)              |                          |    |                       |    | X                           |   | X | X | X  |   |   |         | X | X | X  |                      |                           |
| Fatigue                                |                          |    | X                     |    | X                           |   | X | X | X  | X   |   |         | X | X | X  | X                    |                           |
| Questionnaires                         |                          |    | X                     |    | X                           |   |   |   |    | X   |   |         |   |   |    | X                    | X                         |
| Health Status                          |                          |    |                       |    | X                           |   | X | X | X  | X   |   |         | X | X | X  | X                    |                           |
| Randomization                          |                          |    | X                     |    |                             |   |   |   |    |   | X   |         |   |   |    |                      |                           |
| Blood draw                             |                          | X  |                       |    |                             |   |   |   |    |   | X (same day as, prior to biopsy)                          |         |   |   |    |                      | X                         |

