**Strength by 1-Repetition Maximum (1-RM)** will be used to prepare exercise prescriptions and determine the effects of training. The 1-RM (maximal weight that can be lifted 1 time using correct form through the full range of motion) for upper and lower body RE will be performed at week 2, week 4, , and every 4 weeks through week 16. For participants who surpass the maximal load on a machine, an estimated 1RM will be conducted by having the participant perform as many reps as they can with the maximal load until exhaustion. The Bryzcki formula will then be used to determine the participant's estimated 1RM for that given time point.

**DXA** is the preferred method of assessing body composition. Total body DXA scans will be performed at weeks 0 and 16 on Hologic instruments for measurement of total body mass, lean body mass, and fat mass. The operation of the DXA includes daily measurements of the spine phantom, weekly air scans, and tissue bar scans at least once per month. The reproducibility of DXA measurements was assessed in 40 women and men, aged 23-86 years, measured on 2 occasions over 1 month. The coefficients of variation (CV; mean, 95% confidence interval) for total body lean and fat mass were 0.7 (0.53, 0.83)% and 1.7 (1.32, 2.07)%.

**Randomization.** At the conclusion of Screening Visit 3, participants will be randomized to either HIIT or CME. Randomization sequences will be created by the study statistician ([name]) and will be blocked by age, sex, and site to ensure a similar distribution between exercise arms. Due to observable differences in HIIT and CME, participants and trainers cannot be blinded to the treatment arms.

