**Intervention:** Participants will complete 16 weeks of supervised CME or HIIT 3 days/week in the University of Colorado-Denver Exercise Research Laboratory, at the Prevention Center at Fred Hutch (University of Washington (UW) site, and at the Center of Exercise Medicine at University of Alabama. Participants will be given the option to complete 16 weeks of exercise at a recreational center if travel to the University of Colorado-Denver, University of Washinton, and University of Alabama at Birmingham is difficult. The recreation center must meet certain requirements (see risk section). Our study staff will visit the site in advance to ensure appropriate equipment is available. Any fees for membership will be covered by the study team (paid directly to the recreation center, not to the participant). Weeks 1-2 will focus on familiarization with the exercises at low intensity. These sessions will still occur at the University of Colorado-Denver center even if a participant choses to exercise at a local recreation center for the remainder of the 16 weeks. The intensity and duration of exercise will be progressed over the first 3-8 weeks to reach the individualized goals. The HIIT and CME interventions will be matched for exercise volume using standard equations for estimating caloric expenditure assuming 5 kcal/L O2 and 50 min/session duration for CME to meet the PA guidelines (Table 4). The total exercise time will differ by 8 minutes, but HIIT includes rest intervals and variety, which prior studies have shown is associated with greater enjoyment and physiologic benefits than CME.

**HIIT.** Following a 5-minute warm-up at 50% HRR (Heart rate reserve), high and moderate-intensity exercise bouts will alternate: Five bouts of 4-minute high-intensity exercise (90% HRR) will alternate with four 3-minute bouts of moderate-intensity exercise (50% HRR). The total exercise time will be 42 minutes.

**CME.** Following a 4 minute warm-up at 50%  $\text{VO}_{2\text{peak}}$ , the participant will walk for 50 continuous minutes at 60% HRR^140.

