**Maximal aerobic power (VO2 max).** The measurement of VO2max (or peak) will be used to formulate the prescription for CEx at the screening visit. Increases in VO2max in response to exercise training will also verify that the exercise was of sufficient intensity to induce cardiorespiratory adaptations. During an initial 5-min warm-up, walking speed will be adjusted to elicit a HR that is ~70% of maximal HR (from the screening GXT). Speed will then be held constant and the grade of the treadmill will be increased by 2% every 2 minutes until volitional exhaustion or until the test is stopped (see section 4.1.2b). The O2 and CO2 content of expired air will be measured continuously by open circuit spirometry and averaged every 30 sec using an automated online system (TrueMax 2400; ParvoMedics, Sandy, UT). Objective evidence that VO2max has been attained will include at least 2 of the following: a plateau in VO2 despite an increased energy demand, a respiratory exchange ratio in excess of 1.10, and a maximal HR within 10 beats of the age-predicted value. In the absence of these benchmarks, the maximum measured VO2 will be deemed VO2 peak.

**Muscle strength (1-RM).** Muscle strength will be evaluated as the 1-RM (the maximal weight that can be lifted only 1 time using correct lifting form through the full range of motion) for the upper and lower body REx performed during weeks 1-16. 1RMs will be measured at week 0 and every 4 weeks to week 20. The change in muscle strength from week 0 to 16 will be a secondary outcome measure.

**Exercise Intervention.** Participants will be assigned with equal probability to one of the two exercise intervention arms (high intensity interval training [HIIT] or continuous moderate intensity exercise [CME]) following completion of screening procedures. Randomization procedures will be site-specific, and use permuted blocks with stratification by sex and 10-year age categories (i.e., 50-59 years, 60-69 years, 70-80 years), to assure similar distribution in each arm. The allocation to study arm will remain blinded (masked) to the research assistant conducting the physical function assessments and to laboratory personnel.

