## Analysis Approaches

### Analysis Plan:

**Aims 1 and 2:** Baseline (week 0) characteristics will be compared between groups prior to comparisons of endpoints, with log transformation for normality, as appropriate. Age, sex, baseline CD4 count and/or VACS score, smoking, exercise intensity and body mass index (BMI) will be considered for inclusion into regression models; although if matching and/or balance by age and sex is achieved, these will be precision variables, rather than confounders. Differences in response by antiretroviral therapy (ART) class; prior ART exposure to zidovudine, stavudine, didanosine; use of statin; psychiatric medication burden; and use of hormone replacement therapy will also be explored. Given repeated measurements, a linear mixed effects model will be used with change from week 0 as the primary outcome.

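### The Aims 1 and 2 model leaves out the baseline outcome value and site, makes age and sex optional, lists an undefined exercise-intensity covariate, and does not settle which walk test is the baseline

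*Combined protocol and SAP*

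**What the plan says.** The Analysis Plan for Aims 1 and 2 (under Analysis Approaches) states that "a linear mixed effects model will be used with change from week 0 as the primary outcome". The candidate covariates are age, sex, CD4 count and/or VACS score, and then "smoking, exercise intensity and body mass index (BMI) will be considered for inclusion into regression models". The plan adds that, if balance on age and sex is achieved, those two serve precision rather than control of confounding. The baseline value of the outcome and site do not appear as model terms.

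Allocation does use these factors. Section IV.D (Exercise Intervention) makes randomisation site-specific, to "use permuted blocks with stratification by sex and 10-year age categories". The Randomization paragraph in IV.C and the sample size text in Section F also name site, sex and age. In the same Analysis Approaches section, the main cognitive substudy models include site.

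On timing, IV.C states that "At the conclusion of Screening Visit 3, participants will be randomized to either HIIT or CME". Table 3 puts the full physical function battery, which contains the 400-m walk, and the fatigue assessment at baseline visit 3. It then shows the row beginning "Physical function (BRIEF" (400-m walk and chair rise), and fatigue again, at week 0.

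**The concern.** Four features leave the primary analysis less precise or less definite than it need be.

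- **No baseline value in the model.** An unadjusted change score carries baseline noise that a baseline covariate would remove.
- **Allocation factors omitted or optional.** Site is absent, and age and sex enter only by a later decision. The standard error then tends to be too large, and the final model is open to choice after baseline groups have been compared.
- **An undefined covariate.** The documents describe the randomised contrast itself in terms of intensity: Aim 1 is to "Compare the effects of two exercise regimens varying by interval and intensity", and the Background speaks of changes "in response to two levels of exercise intensity". A variable of that name in a list with smoking and BMI could be a second copy of arm, or the intensity each participant achieved. The second is measured after randomisation and lies on the pathway under test.
- **Two candidate baselines.** One walk and one fatigue assessment come before randomisation and one of each after it. Participants cannot be blinded, the walk depends on effort, and fatigue is self-reported, so the choice is not neutral.

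**Working it through.** **Inputs, all from Section F (Sample Size Calculations) unless noted.** 400-m walk: improvement of 45 s against 20 s (difference 25 s), SD 38 s, rho = 0.7. Fatigue: means 19 and 27, SD 8, rho = 0.5, changes of 27% and 20%. State 3 respiration: mean 580, SD 180, rho = 0.5, changes of 50% against 30%. Two-sided 0.05, two-sample t-test on change, 40 evaluable per group. Randomised total: 180 (Aim 1; Section IV.B).

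**Plan's own figures first (exact two-sample t power, 40 per group).**
- State 3: difference 0.20 × 580 = 116; SD of change 180 × √(2 × 0.5) = 180; power 81.2% (plan: above 81%).
- Morning fatigue: 0.27 × 19 = 5.13, SD 8; power 80.8%. Evening: 0.20 × 27 = 5.4; power 84.6% (plan: above 80% for both).
- 400-m walk: difference 25, SD of change 38; power 82.8%. The plan's figure of above 88% is not reproduced. Reading 38 as a single-visit SD gives a change SD of 38 × √(2 × 0.3) = 29.4 and power 96.3%. Of the readings tried, only the baseline-adjusted SD below comes close. That mismatch is a separate point.

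**Gain from baseline adjustment.** Assume equal variance σ² at the two visits.
- Variance of change: 2σ²(1 − rho). Baseline-adjusted: σ²(1 − rho²). Ratio: (1 + rho)/2.
- rho = 0.7: ratio 0.85, a 15% cut, worth 1/0.85 = 1.18 times the participants.
- rho = 0.5: ratio 0.75, a 25% cut, worth 1/0.75 = 1.33 times the participants.

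| Outcome | Per arm | Change score | Baseline-adjusted |
|---|---|---|---|
| 400-m walk, SD 38 → 38√0.85 = 35.0 | 40 | 82.8% | 88.3% |
| 400-m walk | 180 × 0.8 / 2 = 72 | 97.5% | 98.9% |
| State 3 | 40 | 81.2% | 90.8% |
| Morning fatigue | 40 | 80.8% | 90.5% |
| Evening fatigue | 40 | 84.6% | 93.1% |

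**Site.** No between-site variance is given. If site explains 0 to 10% of the variance of change (assumption), power for the walk at 40 per arm moves from 82.8% to at most 86.5% with site alone, and from 88.3% to at most 91.3% with baseline as well.

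**Exercise intensity, only if it meant achieved intensity.** HIIT is prescribed as follows: "Five bouts of 4-minute high-intensity exercise (90% HRR) will alternate with four 3-minute bouts of moderate-intensity exercise (50% HRR"). Its time-weighted mean is (20 × 90 + 12 × 50)/32 = 75% HRR, against 60% for CME. The arms therefore differ by 15 points on average, or 30 at the HIIT peaks. The within-arm SD is not given; assume 5 to 10 points. The variance of the arm term is inflated by 1 + d²/(4s²):
- d = 15, s = 10: 1 + 225/400 = 1.56.
- d = 30, s = 5: 1 + 900/100 = 10.

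At 40 per arm, power (normal approximation) falls from 83.7% to between 65% and 15%, even if none of the effect acts through intensity. In a 4,000-run simulation (d = 15, s = 10), the 25 s effect shrank to about 12.8 s when half of it acted through intensity, and to about 0 s when all of it did.

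**Which baseline.** IV.C gives DXA at weeks 0 and 16, but Table 3 places the first scan at visit 3. State 3 respiration is listed as a week 0 to 16 change, but the first biopsy and blood draw are at visit 2. The Analysis Plan itself equates baseline with week 0. So week 0 sometimes means the pre-randomisation visits. For the walk and fatigue, however, Table 3 also has a separate week 0 entry, and the label does not say which is meant.

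**The case against.** A change-score analysis of a randomised trial is valid, and leaving out baseline or site does not bias it; preferring adjustment is a matter of efficiency. At the current sample size the gain in primary power is 1.4 points. Chance baseline imbalance is not an extra harm either, because it is already inside the SD of change. All of this stands.

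Two stronger readings are tempting, and the documents support neither.

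- **That the plan will adjust the treatment effect away.** The term is undefined and only a candidate. Elsewhere the documents use it for the compared regimens, including in the list of a priori hypotheses under Rigor and Reproducibility. If it labels arm, it is the term of interest; as a duplicate of arm it would be aliased, not biased. No text names achieved intensity as an analysis variable. The attenuation figures are therefore conditional.
- **That the primary outcome is anchored to a test taken after participants know their arm.** Week 0 is used loosely for pre-randomisation procedures, and no text says when participants learn their allocation. Table 3 shows an ambiguity, not a settled post-allocation baseline.

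Neither answer removes the need to define the covariate and name the baseline. The plan's own site adjustment in the cognitive substudy also suggests that the omission for Aims 1 and 2 was not a deliberate choice.

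**Conclusion.** The point holds as one of precision and specification, not of bias. The model omits the baseline value and site and leaves two stratification factors optional. Baseline adjustment would cut the contrast variance by 15% for the walk and 25% for fatigue and state 3 respiration. These figures rest on the plan's correlations, equal variance at both visits, and a week-16 comparison of two groups, as in the plan's power section. The effect on primary power is 5.5 points at 40 per arm and 1.4 points at 72 per arm, so the trial's main conclusion is not threatened. The undefined intensity covariate and the unnamed baseline are real gaps, because each leaves the primary estimate open to more than one reading. This should be fixed, as a free improvement; it does not invalidate the primary test.

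**What to change.** Prespecify one primary model:

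- **400-m walk:** arm, visit, arm-by-visit, the visit 3 (pre-randomisation) value, site, sex and age category, always included whatever the observed balance, with the contrast read at week 16.
- **Lee Fatigue Scale, morning and evening:** the same form, with the pre-randomisation assessment as baseline.
- **State 3 respiration** (baseline and week 16 only): a week-16 comparison adjusted for the baseline specimen, with site, sex and age category.
- **Covariate list:** remove *exercise intensity* from the primary model. Keep any measure of achieved intensity for a secondary adherence or mediation analysis, and the other listed covariates for exploratory models.
- **Baseline:** state that it is the last assessment before randomisation, and what the week 0 walk and fatigue assessments are for.

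The cost is wording in the analysis plan. Every variable is already collected.
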